### 5.1.4 Phase 2 Primary Endpoint

The primary study endpoint for Phase 2 is ORR, defined as the proportion of subjects achieving a BOR of confirmed PR + CR.

Response will be determined by the investigator assessment according to Response Evaluation Criteria in Solid Tumors (RECIST) 1.1 ([Protocol Appendix F](#)). Detailed rules for deriving BOR are provided in [Appendix 13.1](#). Note that BOR of SD has to be achieved at least  $\geq 7$  weeks after the first dose. All response of CR and PR must be confirmed by repeated scans  $\geq 4$  weeks following the initial achievement of response.

Additional efficacy endpoints (determined by investigator assessment):

- Duration of response (DOR), defined as the time from the date of first documented and confirmed CR/PR until the first documentation of disease progression as determined by the investigator or death, whichever comes first.
- Disease control rate (DCR), defined the proportion of subjects achieving a best overall response of CR, PR, or SD. Note that Non-CR/non-disease progression (PD) will be included for subjects without measurable lesion at baseline ([Appendix 13.1](#)).
- Progression-free survival (PFS), defined as the time from first dose date to the date of the first documentation of disease progression as determined by the investigator or death (whichever occurs first).
- Overall survival (OS), defined as the time from first dose date to the date of death (event) or date last known alive or data cutoff date, whichever comes first (censored).
- Clinical benefit rate (CBR): defined as the proportion of subjects with BOR of CR, PR, or durable SD (duration of SD  $\geq 23$  weeks). For subjects whose BOR is SD, duration of SD is defined as the time from the date of first dose to the date of the first documentation of disease progression or death, whichever occurs first. Note that for subjects without measurable lesion at baseline, timepoint response of Non-CR/non-PD will be considered as SD for analysis purpose ([Appendix 13.1](#)).

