#### 5.4.2 Additional Efficacy Analyses

Additional efficacy analyses will be performed for DCR, CBR, PFS, DOR and OS.

For DCR: estimated DCR and the corresponding Clopper-Pearson 2-sided 95% CI will be presented. The presentation strategy will be similar to the ORR analysis.

For CBR: estimated CBR and the corresponding Clopper-Pearson 2-sided 95% CI will be presented. The presentation strategy will be similar to the ORR analysis.

For PFS: The main analysis of PFS will follow the FDA censoring rule guidance: progression date is assigned to the earliest date when any RECIST 1.1-defined disease progression is

observed without missing more than one adequate radiologic assessments. Details are included in [Appendix 13.2](#).

The distribution of PFS will be estimated using Kaplan-Meier methodology. Median PFS and the corresponding 2-sided 95% CIs will be summarized by treatment groups, *ESR1* mutation groups, or PgR status. The PFS rate at 3, 6, 9, and 12 months will be estimated using the Kaplan-Meier Method and the corresponding 2-sided 95% CIs will be summarized. In addition, Kaplan-Meier plots of PFS will be presented.

In addition to the main PFS analysis, supportive analysis may be performed (specified in [Appendix 13.2](#)): 1) considering new anticancer therapy as events, 2) allowing subjects to have events after COVID-19 related censoring, 3) considering clinical PD as events.

A complete list of PFS analysis is included in Table 2:

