**Table 2 List of PFS analyses**

Purpose	Analysis set	Presentation grouping [Table, Figure]
Protocol defined	FAS	Treatment groups [TF]
Protocol defined subgroup	FAS CCI [REDACTED]	ESR1 status (Mutant, Wild type) [T]
CCI [REDACTED]	[REDACTED]	[REDACTED]
[REDACTED]	[REDACTED]	[REDACTED]
[REDACTED]	[REDACTED]	[REDACTED]
[REDACTED]	[REDACTED]	[REDACTED]
[REDACTED]	[REDACTED]	[REDACTED]
Sensitivity analysis is not included in the table and will be detailed in TLG shells.		
ESR1 = estrogen receptor, F = figure, FAS = Full Analysis Set, G = graph, PFS = progression-free survival, PgR = progesterone receptor, T = table.		

For DOR, the analysis will include subjects with confirmed responses. The same logics in censoring rules as those for primary analysis of PFS will be applied. If there are  $\geq 7$  subjects with confirmed responses, the median of DOR will be estimated using Kaplan-Meier methodology; median DOR and the corresponding 2-sided 95% CI will be presented by treatment groups on RES. If there are  $< 7$  subjects with confirmed responses, DOR will be listed.

For OS, the distribution of OS will be estimated using Kaplan-Meier methodology. Median survival time and the corresponding 95% CI, survival rates at 6, 12, 18, 24, 30 and 36 months, and corresponding 95% CIs will be estimated using Kaplan-Meier method. The analysis will be presented by treatment groups, *ESR1* mutation groups, and PgR status.

In addition, waterfall plot of best percentage change may be provided for RES subjects started on the 450 mg dose and color-coded by *ESR1* mutation groups.

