## 13 APPENDICES

### 13.1 General Rules Deriving Best Overall Response

The BOR is determined once all the data for the subject is known. For this study, a confirmation of complete responses or partial responses is required  $\geq 4$  weeks after the initial assessment of response. In order for SD to be considered the BOR, it must occur  $\geq 7$  weeks following the first dose of study drug. For subjects who do not have a target lesion at baseline, a timepoint response of Non-CR/Non-PD will be treated as SD in BOR derivation, and will be included in DCR and CBR calculation.

To program the BOR per RECIST, the rules below will be followed:

1. The tumor response data collected via the CRFs will be used
2. Any further response assessments after the first PD identified will not be considered for the BOR determination, however they will be presented in the data listings
3. Any tumor assessments after the subject starts a new anti-cancer therapy will not be considered
4. If there are 2 or more consecutive missing adequate tumor assessments, all subsequent assessments will not be considered for the determination of BOR.

Note that the duration between 2 adequate tumor assessments, as well as the duration between the last adequate tumor assessment and death or PD, will be used to identify the cases where 2 or more consecutive tumor assessments are missing. Using the start day and the end day to denote the study days of the two endpoints of the duration, duration = end day – start day. If the duration is longer than  $16\text{ weeks} + 2 \times 7\text{ days}$  (tumor assessment window) – 1 day (ie, 125 days), then it is considered that 2 or more consecutive adequate tumor assessments are missing.

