**Table 6 General Rules Deriving BOR per RECIST 1.1**

Timepoint 1 Overall Response	Timepoint 2 $(\geq 4\text{ weeks sinceTimepoint 1})$ Overall Response	BOR b
CR	CR	CR
CR	PR	SD, PD or PR  If a CR is truly met at first time point, then any disease seen at a subsequent time point, even disease meeting PR criteria relative to baseline, makes the disease PD at that point (since disease must have reappeared after CR). Best response would depend on whether minimum duration for SD was met. However, sometimes 'CR' may be claimed when subsequent scans suggest small lesions were likely still present and in

		fact the subject had PR, not CR at the first time point. Under these circumstances, the original CR should be changed to PR and the best response is PR.
CR	SD/PD	SD if duration of SD $\geq$ 7 weeks, otherwise PD
CR	NE	SD if duration of SD $\geq$ 7 weeks, otherwise NE. In a special case, if CR is at the next timepoint after NE, BOR will be CR.
CR a		SD if duration of SD $\geq$ 7 weeks, otherwise NE
PR	CR/PR	PR
PR	SD/PD	SD if duration of SD $\geq$ 7 weeks, otherwise PD
PR	NE	SD if duration of SD $\geq$ 7 weeks, otherwise NE. In a special case, if PR or CR is at the next timepoint after NE, BOR will be PR.
PR a		SD if duration of SD $\geq$ 7 weeks, otherwise NE
SD	Any response	SD if duration of SD $\geq$ 7 weeks, otherwise PD
PD		PD
NE		NE if the subject did not have a post-baseline tumor assessment, or if the subject only had one post-baseline tumor assessment of an early SD (duration < 7 weeks) as the overall response, or post-baseline tumor assessments are not evaluable (ie, recorded as 'NE' as overall responses via the CRF)
UNK		UNK if the subject did not have a baseline tumor assessment

BOR = best overall response, CR = complete response, CRF = case report form, NE = not evaluable, PD = disease progression, PR = partial response, RECIST = Response Evaluation Criteria in Solid Tumors, SD = stable disease, UNK = unknown.

a: If this was the only tumor response assessment (eg study treatment was discontinued).

b: For subjects who does not have target lesion at baseline, a timepoint response of Non-CR/Non-PD will be treated as SD in BOR derivation.

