**Table 7 Censoring Rules for the Derivation of PFS in Primary Analysis**

No.	Situation	Date of Event (Progression/Death) or Censoring	Outcome
1	No baseline or post-baseline tumor assessments	Date of first dose	Censored
2	Progression documented between scheduled visits	Date of first radiologic PD assessment	Event
3	No progression at the time of data cutoff	Date of last adequate radiologic assessment prior to or on date of data cutoff	Censored
4	New anticancer treatment started	Date of last adequate radiologic assessment prior to or on date of new anticancer treatment	Censored
5	Death before first PD assessment	Date of death	Event
6	Death between adequate assessment visits a	Date of death	Event
7	Death or progression after more than one missed visit/tumor assessment b	Date of last adequate radiologic assessment before missed tumor assessments	Censored

CR = complete response, PD = disease progression, PFS = progression-free survival, PR = partial response, SD = stable disease.

a Adequate tumor assessment is radiological assessment of CR, PR, SD, non-CR/non-PD or PD as determined by investigators at regular interval as defined in the protocol. Any tumor assessments after new anticancer treatment starts will be removed in the definition of PFS.

b Defined in [Appendix 13.1](#).

The priority of the censoring rules is as follows:

1. If the subject had PD or death, the following sequence will be applied:
  - If a subject did not have a baseline tumor assessment (No. 1), the subject will be censored on the date of first dose. If the subject died within 125 days following first dose and did not receive a new anticancer treatment, it will be counted as an event at the date of death. If a subject had new anticancer treatment before PD or death (No. 4), the subject will be censored on the date of the last adequate tumor assessment prior to or on the date of new anticancer treatment.

- If a subject missed two or more tumor assessments (>125 days) before PD or death (No. 7), the subject will be censored on the date of the last adequate tumor assessment before PD or death. Note that if a subject is censored by both this criterion and the anticancer treatment criterion, the earliest censoring date will be used.
- Otherwise, if a subject had an event (No. 2, No. 5, or No. 6), the earliest event date will be used.

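### Duration of stable disease for CBR has no rule for new therapy or missed scans, so subjects whose PFS is censored at week 8 can count as clinical benefit

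*SAP*

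**What the plan says.** Section 5.1.4 defines CBR as the "proportion of subjects with BOR of CR, PR, or durable SD", with durable meaning at least 23 weeks. Where SD is the best response, "duration of SD is defined as the time from the date of first dose to the date of the first documentation of disease progression"; an earlier death also ends it. The only appendix cited there is 13.1, which derives best overall response.

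The analysis text in Section 5.4.2 adds an interval and a presentation format: "For CBR: estimated CBR and the corresponding Clopper-Pearson 2-sided 95% CI will be presented". It gives no event or censoring rule.

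The two neighbouring endpoints do have such rules:

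- **PFS** (Appendix 13.2, priority list under Table 7): "If a subject had new anticancer treatment before PD or death (No. 4), the subject will be censored" at the last adequate assessment up to that treatment. Likewise, "If a subject missed two or more tumor assessments (>125 days) before PD or death (No. 7), the subject will be censored" at the last adequate assessment before the event.
- **DOR** (Section 5.4.2): "The same logics in censoring rules as those for primary analysis of PFS will be applied".

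Appendix 13.1 does mention new therapy, but only for the response derivation: "Any tumor assessments after the subject starts a new anti-cancer therapy will not be considered". Its rule 4 on missed scans is likewise confined to determining best overall response.

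**The concern.** For a subject whose best response is SD, duration of SD has the same start and the same stated end as PFS, yet only PFS receives rules for what happens in between. Scans stop at new anticancer therapy (Section 5.4), so for a subject who switches without documented PD, the next event that can end duration of SD is usually death. That death may come long after disease control was last shown, while the subject is on another drug. The printed definition credits the whole interval to the study drug.

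The rule is also uneven. A subject who switches at week 10 and dies at week 30 gets a 30-week duration. The same subject alive at data cutoff has no end date at all.

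CBR is named in the Phase 2 primary objective (Section 3.1.4) and is analysed by subgroup (Section 5.4.3). The error from crediting deaths after new therapy goes only upward, and CBR and PFS can tell different stories about the same subject.

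**Working it through.** **Inputs from the SAP.** Scans every 8 weeks (Section 5.4). SD must be seen at 7 weeks or later to be the best response, and durable SD means at least 23 weeks (Section 5.1.4). The missed-assessment limit is 125 days (Appendix 13.1). Data cutoff is 6 months after the last subject's first dose (Section 3.2).

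**Reproducing the SAP's limit.** 16 × 7 + 2 × 7 − 1 = 125 days, as stated. The other two limits are scheduled scans less the 7-day window: (56 − 7)/7 = 7 weeks and (168 − 7)/7 = 23 weeks.

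**Case (a): new therapy, then death.** SD at week 8 (day 56), new therapy at week 10, death at week 30 (day 210).
- Best response: SD, since 8 ≥ 7 weeks.
- Duration of SD as printed: 30 weeks ≥ 23, so clinical benefit.
- PFS: censored at week 8 under No. 4.
- Appendix 13.1 rule 3 changes nothing, because a death is not a tumor assessment.

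**Case (b): missed scans, then PD or death.** SD at week 8, no scan afterwards, PD or death at week 30, no new therapy.
- Gap: 210 − 56 = 154 days > 125.
- PFS: censored at week 8 under No. 7.
- Duration of SD as printed: 30 weeks, so clinical benefit.

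Case (b) is bounded. With the last scan at week 8, No. 7 applies only to events after 56 + 125 = 181 days (week 25.9). With the last scan at week 16, it applies after 112 + 125 = 237 days (week 33.9). Earlier events are valid PFS events and there is no conflict. In case (a), a death at weeks 23 to 25 after a day-56 scan is caught by No. 4 alone.

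**Size, case (a) only; all inputs below are assumed.** New therapy at week 10; exponential survival from then with median 12 to 30 months. The share of such subjects with a death recorded between week 23 and follow-up week F is S(13) − S(F − 10), with S(t) = exp(−ln 2 × t / median) and t in weeks. The shortest follow-up is that of the last subject enrolled: 6 × 30.4375 = 182.6 days = 26.1 weeks.

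| Follow-up F | Median 12 mo | 18 mo | 24 mo | 30 mo |
|---|---|---|---|---|
| 26.1 weeks | 3.4% | 2.4% | 1.9% | 1.5% |
| 52 weeks | 26.9% | 20.2% | 16.1% | 13.3% |
| 104 weeks | 55.5% | 45.6% | 38.2% | 32.6% |

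If 2% to 5% of a group have SD and then switch without PD (assumed), multiplying gives the overstatement of CBR:
- F = 26.1 weeks: 0.03 to 0.17 points
- F = 52 weeks: 0.27 to 1.35 points
- F = 104 weeks: 0.65 to 2.77 points

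**The case against.** The best counter-argument is that the PFS definition in Section 5.1.4 is just as bare. It too runs from first dose to PD or death, and its censoring appears only later. Since duration of SD is the same interval, an analyst may well reuse the PFS derivation, and Sections 8 and 9 leave further rules to specifications that are not shown. Table 6 also applies an SD duration to subjects with a single scan, for example one who "only had one post-baseline tumor assessment of an early SD", so the SAP does not always use the term in its strict sense. For a late PD after missed scans, an analyst following Appendix 13.1 rule 4 might drop the scan. Finally, case (a) needs a recorded death. Section 3.2 describes survival follow-up after progression and does not expressly cover subjects who switch without it, although the OS analysis suggests their deaths are sought.

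These points show that the rule might be repaired in programming. They do not show that the SAP repairs it. The SAP states its censoring rules for PFS and expressly carries them to DOR, which makes the silence on CBR a real gap. Neither rule in Appendix 13.1 removes the death at week 30. The provision treating unknown response as non-response (Section 5.3.5) does not help either, because a best response of SD is known. What does stand is that the pattern is narrow, the endpoint is an additional one, and the effect is probably small.

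**Conclusion.** The concern holds. As printed, the CBR definition counts as durable SD some subjects whose disease control was last shown at week 8 or 16 and whose PFS is censored there. The classification in the two worked cases follows from the SAP's own rules and needs no assumption.

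The size does need assumptions. How many subjects are affected cannot be derived from the SAP. For the new-therapy case the illustration gives about 0 to 3 percentage points, depending on assumed survival, follow-up and the assumed 2% to 5% prevalence. The missed-scan case is not quantified. Each misclassified subject adds 100/N points, so a single case weighs more in a small *ESR1* group. ORR and its hypothesis tests are untouched. This should be fixed, but it does not threaten the primary analysis.

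**What to change.** Add one rule to the CBR definition in Section 5.1.4, or to the CBR paragraph in Section 5.4.2, in the way the SAP already does for DOR:

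- Duration of SD follows the Table 7 event and censoring rules, with PD dated as for PFS.
- Without a valid PD or death, including ongoing SD at cutoff, it ends at the last adequate assessment.
- A subject with best response SD whose duration so derived is below 23 weeks, whether event or censored, is not counted as clinical benefit.

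This works at the planned cutoff. The latest in-window week-24 scan falls at week 25, before the 26.1 weeks available for the last subject enrolled, so ongoing SD scanned on schedule keeps its credit. Both worked cases would then end at week 8 and not count.

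The cost is a short text change and reuse of the existing PFS derivation. Reported CBR may be slightly less favourable.

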### 5.1.5 Phase 2 Secondary Endpoint(s)

Secondary study endpoints for Phase 2 are:

- Safety/tolerability: same as Phase 1.
- Further characterize PK of H3B-6545.
- Evaluate the effect of a high-fat meal on the relative bioavailability of H3B-6545.
- Endometrial thickness and uterine volume in a subgroup of subjects.
- Effect of H3B-6545 on serum bone turn-over markers, namely BSAP (for osteoclast metabolism), PINP (for bone formation), and CTX (for bone resorption).

[figure not shown]
## 5.2 Study Subjects

### 5.2.1 Definitions of Analysis Sets

Analyses will be performed using the following analysis sets:

- **Full Analysis Set (FAS)**, which will consist of all subjects who receive at least 1 dose of study drug.
- **FAS with Known *ESR1* Status**, which will consist of all subjects who receive at least 1 dose of study drug and have known *ESR1* status per sponsor approved laboratory analysis of cfDNA. Subjects with unknown *ESR1* status will be excluded. This analysis set will be used for two types of analysis:
  - Analysis by *ESR1* mutation groups: clonal Y537S, clonal D538G, clonal Y537S or clonal D538G, polyclonal Y537S and D538G, Y537S and D538G negatives
  - Analysis by *ESR1* mutation status: mutant versus wild type: *ESR1* mutant group includes any mutation at an AF  $\geq 0.05\%$  (ie, limit of detection); *ESR1* wild type group include any mutation at an AF  $< 0.05\%$ .
- **Safety Analysis Set**, which will consist of all subjects who receive at least 1 dose of study drug. This will be the analysis set for all safety evaluations except DLT results.
- **Dose Evaluable Set**, which will consist of all subjects who were evaluable for DLT in Cycle 1 of Phase 1, as collected on case report form (CRF) page. This will be the analysis set for DLT results. Note that subjects who do not receive study drug for at least 70% of the planned dose of H3B-6545 during the first cycle (28 calendar days) for reasons not considered to be a DLT by both the investigators and the Sponsor will be replaced; the subjects who are replaced will not be considered evaluable for DLT assessments ([Protocol Section 10.11.5](#)).
- **PK Analysis Set**: This analysis set will be derived and reported in a separate PK analysis report.
- **Food-effect Analysis Set**: This analysis set will be derived and reported in a separate PK analysis report.

CC1

- **Response Evaluable Set (RES)**, which will consist of those subjects who receive at least 1 dose of study drug and have measurable disease at baseline and at least 1 post-baseline adequate evaluation. This will be the primary analysis set for efficacy evaluations.
- **Endometrium Safety Evaluable Set**, which will consist of those subjects with intact uteri at baseline, who receive at least 1 dose of study drug and have ultrasound assessments at screening/baseline and three months after starting trial therapy.

- **Bone Turnover Markers Evaluable Set**, which will consist of those subjects who have baseline/screening assessments of bone turnover markers and at least one additional assessment at 6 and/or 12 weeks after starting trial therapy. To be included in this set, subjects must have received trial therapy uninterrupted for at least 14 days prior to 6-week or the 12-week assessment.

### 5.2.2 Subject Disposition

The number and percentage of subjects enrolled (ie, those who signed informed consent) along with reason for screen failure will be summarized.

The number of subjects in each analysis set will be summarized. The number and percent (based on FAS) of subjects who completed/discontinued treatment will be summarized by treatment groups, along with the primary reason for discontinuation.

### 5.2.3 Protocol Deviations

All important protocol deviations will be determined prior to database lock and will be agreed upon by a cross-functional team review of individual subject data. The summary table and listing of important protocol deviations will be provided using data in the clinical database.

All important protocol deviations will be listed and summarized descriptively.

### 5.2.4 Demographic and Other Baseline Characteristics

Demographic and baseline characteristics for the FAS will be summarized by treatment groups using descriptive statistics. Continuous demographic and baseline variables include age (year), weight (kg) and height (cm); categorical variables include age group ( $\geq 18$  to  $<65$ ,  $\geq 65$ ) sex (male, female), race (White, Black or African American, Asian [Japanese, Chinese, Other Asian], American Indian or Alaska Native, Native Hawaiian or other Pacific Islander, and Other), Ethnicity (Hispanic or Latino, Not Hispanic or Latino), Eastern Cooperative Oncology Group Performance Status (ECOG PS), measurable disease at baseline, bone disease without measurable lesion at baseline (defined by subjects without measurable disease and with non-target bone lesion presented at baseline).

Disease history will be summarized by treatment group:

- Time from tumor diagnosis to date of the first dose (months)
- Age at diagnosis (years) summarized both descriptively and by categories ( $<65$ ,  $\geq 65$ )
- Location of primary tumor site
- Tumor staging using TNM classification

Disease characteristics at study entry will be summarized by treatment groups (based on FAS), and baseline *ESR1* mutation groups (based on FAS subjects who started on 450 mg)

- Metastatic sites at baseline

- Mutation status of *ESR1*, *PIK3CA* (phosphatidylinositol-4,5-bisphosphate 3-kinase catalytic subunit alpha), *AKT1* (AKT serine/threonine kinase 1) at baseline
- Progesterone Receptor (PgR) status and positivity as percentage of PgR positive cells at baseline.

Previous anti-cancer medications will be summarized by treatment groups (based on FAS) and baseline *ESR1* mutation groups (based on FAS subjects who started on 450 mg):

- Number of previous anti-cancer regimens containing endocrine therapies in locally advanced/ metastatic disease settings
- Number of previous anti-cancer regimens not containing endocrine therapies in locally advanced/ metastatic disease settings
- Therapeutic setting of previous anti-cancer regimens
- Type of previous anti-cancer regimens (endocrine, including fulvestrant, aromatase inhibitor (AI), tamoxifen and other, CDK4/6 inhibitor, chemotherapy, other; CDK4/6i and AI; CDK4/6i and fulvestrant) in locally advanced/ metastatic disease settings

Previous radiotherapy will be summarized by treatment groups (based on FAS):

- Number of subjects having prior radiotherapy
- Last radiotherapy site
- Tumor lesion at the site progressed since last radiotherapy
- Time (in month) from end of last previous radiotherapy to first dose of study drug

Listings of demographics, baseline characteristics, disease history and characteristics, previous anti-cancer medications and previous radiotherapy will be provided.

Medical history and current medical condition:

Medical history and current medical condition, as recorded on the CRF, will be listed. Reported medical conditions will be coded using Medical Dictionary for Regulatory Activities (MedDRA), version 19.0 or later.

